## **Introduction to the study:**

Stroke is the leading cause of disability worldwide, and predictions indicate that the prevalence of stroke will continue to rise. Impairments resulting from stroke lead to mobility deficits in the lower limb, affecting gait. Symmetry is a critical component to describe the characteristics and overall skilled quality of gait, specifically in respect to reductions in walking speed and limitations in endurance and the flexibility to adapt to different environmental contexts. Asymmetries between the paretic and non-paretic limb exist in spatial and temporal parameters of gait as well as in load force production of the limbs. Increases in load force of the paretic limb (improved symmetry) have been correlated with gains in temporal gait parameters as well as improved modulation of gait speed.

Traditional care models have focused on improving gait velocity and reducing asymmetry in a post stroke population, however despite efforts, there is questionable carry over into community participation activities and individuals are left with residual deficits. Body-weight supported treadmill training (BWSTT) has been used to increase gait velocity and remediate asymmetries in this population. BWSTT can provide training at a higher intensity (number of steps per therapy session) than can be achieved in traditional overground care models, with a greater reproducibility of step kinematics. Further, the task-specific nature of this training makes BWSTT appealing. However, despite these benefits, BWSTT has not proven to be more efficacious than traditional training.

Robotic devices have also been used to improve gait velocity and symmetry. These devices share many of the same promising design features as BWSTT including providing a higher intensity training with a greater kinematic reproducibility of stepping parameters than do traditional care models. Also, similar to BWSTT, these devices do provide training that

is task-specific in nature. However, despite best efforts, robotic-based gait training devices have been shown to have effects similar to conventional care models. This is likely due to employing guided assist control models that render robotic treatments more passive than active on the part of the user. These training paradigms can be beneficial in the early stages of learning, as they provide the learner with information about an 'ideal' or desired pattern that can be used as a reference for future movements in the development of the motor program. However, a drawback of guided assist control is that if the guidance is not reduced over the course of training, users can become dependent on the guided feedback they receive from the system, which improves performance, but can lead to reduced retention.

The tethered pelvic assist device (TPAD) is a novel robotic device that uses an arrangement of force tethers attached to a pelvic belt to manipulate load forces on the pelvis. In contrast to other robotic devices, the TPAD does not move or guide the limb to a target position during gait tasks, but maintains a prescribed force or guided assist at the level of the pelvis to increase loading onto the paretic limb while the user freely controls the spatiotemporal aspects of limb movement. This allows the user to play an active role during training, rendering the TPAD an ideal device to explore various training paradigms while promoting a sufficient training intensity to drive motor learning and maximize the effects of gait training.

#### **Rationale for current trial:**

A detailed description of the TPAD can be found in the Standard Operating Procedures Manual. Prior experiments have used the TPAD to improve loading onto the paretic limb in a post-stroke population. Initial studies using the TPAD in this population delivered a short duration of TPAD training that provided guided loading directly onto the paretic limb during a single training session. Measures of perceived exertion using the Borg Scale were recorded, as

was the number of falls sustained during study participant. Results showed no falls and Borg Scale measures indicated this was a feasible training paradigm for individuals post-stroke. Further, results also demonstrated that participants were able to increase loading onto the paretic limb during training, and these gains were maintained even when TPAD forces were removed during a post-training interval on the treadmill. However, gains made on the treadmill did not transfer to improvements in overground spatiotemporal gait measures.

A follow up experiment looked at the effects of TPAD training in two different training paradigms over the course of a five-day training. For this study, the TPAD tethers were arranged to apply a horizontal force in the anterolateral direction to induce a weight shift onto the limb during the stance phase of gait without downward forces that passively increase loading onto the limb. Similar to the previous study, the goal of the TPAD training was to improve load symmetry between the two limbs. In addition to the application of TPAD forces, augmented visual feedback was supplied during the course of the training period. This feedback reflected the amount of loading onto the paretic limb in real time and provided a visual representation of the task goal. While the details of the two training paradigms will not be discussed here, results were equivocal between the two paradigms. Both training paradigms showed improvements in load forces on the paretic limb, and thus improved load symmetry between the two limbs. Further, in both training paradigms these improvements were retained after force tethers were removed on the treadmill. However, neither of these training models proved effective at promoting transfer of increased load force symmetry from treadmill training to gains in overground spatiotemporal gait parameters.

Results from these prior studies suggest that TPAD training in a post-stroke population is feasible in regards to safety and tolerance to treatment. Further, TPAD based training has

demonstrated limited preliminary efficacy in improving loading onto the paretic limb and reducing load force asymmetry. However in both studies, participants were not able to transfer gains in load symmetry to overground spatiotemporal measures. In the initial study using the TPAD device, the haptic guidance received specifically directed limb loading onto the paretic side minimizing the active engagement from the user in the training process. Further, this training was provided over the course of single, short duration training session. In the following study, modifications were made to configure TPAD tethers in a way that provided guidance to weight shift over the affected limb, while still enabling the user to play an active role in the training process. Further, visual feedback was also provided to further engage the user during training. However, this visual feedback was not faded over the course of the five-day training. It is plausible that the gains seen on the treadmill were mitigated by the lack of fading, limiting transfer to overground measures.

Other studies have incorporated a short bout (5-10 minutes) of over ground training to reinforce the goals of the treadmill based intervention. It is plausible that the task-specific nature of over ground training is critical to promote transfer of treadmill training to overground. For the current experiment, visual guidance will be faded over the course of training to promote symmetry during a retention period in which tethered forces are removed. Further, we will also integrate an overground training component reinforcing weight shift onto the paretic limb in an effort to promote transfer of improved load symmetry to overground spatiotemporal gait parameters.

### **Study Objectives:**

The chief purpose of this study is to evaluate the overall feasibility of implementing a five-day, treadmill-based TPAD training with faded visual feedback and an additional task

specific over ground training component to reduce asymmetry in individuals with chronic stroke (> six months after incident).

### **SPECIFIC OBJECTIVES:**

1) Is this five-day intervention using the TPAD and incorporating faded visual feedback and overground walking feasible in terms of safety, treatment tolerance and adherence in individuals with chronic stroke who present with gait asymmetry?

As a measure of treatment efficacy, this study will specifically address the following questions:

2) Is this treatment paradigm effective at improving load force symmetry over the course of five training sessions as measured from Baseline Day one to Post Training Day five?

3) Is this training paradigm effective to promote transfer and improve stance time symmetry in over ground gait as measured from a mean of the three days in Pre Testing to Post Testing?

The presence of preliminary efficacy in the prior two questions, coupled with measures of safety, treatment tolerance and adherence will be used to answer the over arching question of feasibility and preliminary efficacy.

[figure not shown]

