An engineer trained in the use of the TPAD will be present and record data while the physical therapist is supervising the participant during the treadmill portion of the intervention.

Data collected from baseline (Intervention Day 1) and post training (Intervention Day 5) will be used as a primary outcome of vertical Ground Reaction Force (GRF)**. Daily measures (Baseline to Post Training within day) will be used as secondary measures of GRF over the course of training.

Procedures are as follows:

- Reflective markers, safety harness, pelvic belt and arm sling will be placed as described in 'Intervention' section above.
 - The participant will be assisted onto the dual belt treadmill and confirmed gait speed established as described in 'Intervention' section above.
 - Force plates embedded under the dual belts of the treadmill will be activated for data recording of Forces in the vertical direction (F_z) as a measure of GRF. These recordings will occur during minute 1, 3 and 5 during 'Baseline' gait procedures as described in the 'Intervention' section above.
 - RPE** and HR** will be recorded before (at resting) and after 'Baseline' gait, at 10-minute intervals during TPAD force intervention, on completion of 'Post Training' gait, and lastly on completion of overground gait. These measures will be recorded on CRF_TPAD_Form_02.
 - Force plates will also be activated for data collection of F_z as a measure of GRF during minutes 1, 3, 5, 7, 9 of 'Post Training' gait procedures as outlined in the 'Intervention' section above.
 - These procedures will be repeated during daily intervention sessions.
- This will complete the Treadmill Assessment portion.**

D. Intervention

All interventional procedures are to be performed during week two of study participation. These sessions will occur daily for five consecutive days. The duration of each interventional session will be approximately one and one half hours (90 minutes).

[figure not shown]
Participants will be asked to wear gym shorts and comfortable walking shoes for each training session. If participants wear other clothing to the session (e.g. in winter months), they will be given the opportunity to change clothes prior to initiating any study procedures.

A licensed physical therapist will supervise all training sessions. Engineers experienced in operating the TPAD will be primarily responsible for the operating and running of the TPAD and treadmill during the training session.

1. Set up

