- c. During this time the participant will gain familiarity with treadmill walking (Baseline), and vertical force measures (Fz) will be recorded. This is explained in detail in the 'Assessments' section.
- d. Video recordings will be taken from a posterior view during minutes 3-4 of baseline gait.
- e. On completion of the five minutes of baseline gait, the supervising therapist will verbally tell the patient to hold on to the side hand rails, and the treadmill will be stopped.
- f. HR and RPE will be recorded on CRF_TPAD_Form_02 (See attached).
- g. Tethers will be attached to the pelvic belt.
- h. Participants will be offered a seated rest break. Time of rest break will be recorded.
- i. Reflective markers will be placed on the tethers at the point of attachment to the pelvic belt and at the level of the pulley/frame.

- j. A force of resting magnitude will be applied during static standing (enough force to keep tethers taut during gait, but this resting magnitude will be evenly distributed among the four force tethers along a horizontal plane at left/right anterior/posterior positions).
- k. A still image will be taken to ensure tethers are appropriately in place, and markers attached to tether attachment points will be removed.
- l. Once forces tethers are taut, the visual feedback monitor will be turned on and the supervising therapist will explain the role of feedback during the training.
 - Verbiage to be used:
 - “Do you see the 2 bars in front of you? The right/left (side of the paretic limb) represents your weaker leg. This bar moves depending on how much weight you put into your leg. Go ahead and lift your leg so you can see the bar move.”*** [Participant lifts leg and bar representing paretic limb lessens].
 - “Do you see the other bar? It is your target. On each step, I want you to try and get your right/left (paretic) bar up to the top of that target and keep it there as long as possible while you are walking. Do you have any questions?”*** [Participant is given an opportunity to ask questions for which a member of the research team will respond appropriately.]
 - “There will be points during training where this screen isn’t on. I still want you to think about the screen and put as much weight on your weaker leg and keep it there as long as possible – even when you do not see the screen. Do you understand?”***

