#### **2. Efficacy**

There will be two primary measures of preliminary efficacy. First, we aim to establish treatment efficacy on the treadmill. Additionally, we aim to determine whether individuals will

be able to transfer gains to improve symmetry in over ground parameters. Specific outcomes are as follows:

**2.1** The primary outcome measure for efficacy of training on the treadmill will be the calculated load force symmetry ratio as measured load force recorded during Baseline and Post Training on the treadmill with embedded force plates.

**2.2** The primary outcome measure for efficacy of transferability will be the stance symmetry ratio calculated from percentage of time in spent in stance phase of the gait cycle. This will be extracted from data provided by APDM® inertial sensors and measured by the mean of the Pre Test visits to Post Testing.

**2.3** Secondary measures of preliminary force efficacy will include within day changes in load force symmetry as taken on the treadmill. As secondary outcomes to evaluate for transfer of the intervention to overground gait, APDM® inertial sensors will be used to record the percentage of time spent in double support, time in swing phase, stride length, and stride velocity. Symmetry ratios will be calculated for percentage of time in swing phase of the gait cycle, and stride length. Gait velocity as a measure of time performing the 10MWT will also be recorded. Lastly, as an additional balance measure, we will also use the total score of the Berg Balance Scale (BBS).

See Table 1 for a detailed list of measures recorded.

Table 1. All outcome variables and time points at which they will be measured.

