#### ***2.2.1 Load Force (Fz)***

Mean values of Fz Symmetry Ratios will be compared over the course of the five-day training. Specifically, after normality is tested, either a Wilcoxon Signed Ranks test or a paired t test will be used to examine ratio values from the mean of Baseline Day one

to Post Training Day 5. These values will be reported with the associated level of significance. Effect sizes and 95% confidence intervals will also be calculated and reported in the final report. Results will also be presented graphically.

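### The load-symmetry primary (Day 1 Baseline to Day 5 Post Training) adds a same-session change to the between-day change, and no test or interval is planned for the between-day part

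*SAP*

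**What the plan says.** SAP section 2 (Efficacy) states: "There will be two primary measures of preliminary efficacy". Load force symmetry on the treadmill is one of them. Three places agree on its contrast:

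- SAP Specific Objectives, question 2: improvement "over the course of five training sessions as measured from Baseline Day one to Post Training Day five".
- Protocol VI.C.ii (Treadmill Assessments): "Data collected from baseline (Intervention Day 1) and post training (Intervention Day 5) will be used as a primary outcome".
- SAP 2.2.1: a paired t test or Wilcoxon signed ranks test "will be used to examine ratio values from the mean of Baseline Day one" to Post Training on Day 5.

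On the start point, Protocol VI.D.2 step c says of the five-minute Baseline walk: "During this time the participant will gain familiarity with treadmill walking (Baseline), and vertical force measures (Fz) will be recorded". The end point is the ten-minute walk without tethers that follows the 40-minute tethered bout and an offered rest on Day 5.

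SAP 4.2.1 has load recorded at Baseline and Post Training on every training visit. SAP Table 1 shows no load measurement in the pre-test week or at follow-up. SAP 3.1 plans comparisons of Baseline with PT1 to PT4 on the same day, plus daily descriptive means. The regressions over time in SAP 2.2.2 and 3.2 to 3.8 are for overground and balance outcomes, not load.

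**The concern.** Question 2 is about what five sessions achieve. The planned contrast starts from the first Baseline walk and ends minutes after a tethered bout. It therefore includes any short-lived after-effect of the Day 5 session, and any shift from getting used to the treadmill, along with whatever was learned across days.

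The SAP's own rationale makes an after-effect plausible. After a single short session in the initial study, paretic loading rose and "these gains were maintained even when TPAD forces were removed during a post-training interval on the treadmill". With no control arm, nothing else in the design separates these sources.

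At stake is how a positive result is read. The Specific Objectives use it to answer the efficacy question, and the sample size section says the study's results will size later trials. A same-session effect read as accumulated training benefit would pass into both.

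**Working it through.** **Inputs from the documents.** Twelve are enrolled and about 10 are expected to complete (12 × 0.8 = 9.6). Significance is at 0.05; sidedness is not stated, so two-sided is assumed. No SD, effect size or power is given for load symmetry, so there is no planned power figure to reproduce.

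**Decomposition.** Let BL and PT be a participant's Baseline and Post Training symmetry ratios. Then

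PT(Day 5) − BL(Day 1) = [BL(Day 5) − BL(Day 1)] + [PT(Day 5) − BL(Day 5)].

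The first bracket is between-day change, including any familiarisation. The second is the Day 5 same-session change. The primary test sees only the sum.

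**Which analysis covers which part.**

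| Part | Planned analysis for load |
|---|---|
| Sum | SAP 2.2.1: test, effect size, 95% CI |
| Day 5 same-session | SAP 3.1: test, effect size, 95% CI at each of PT1 to PT4 |
| Between-day, Baseline to Baseline | Daily means and graphs only |

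**Size, under assumptions.** Take n = 10 and independent occasion errors with SD σ, so the paired difference has SD σ√2. For a mean shift δ, d = δ/(σ√2). The paired t test has 9 degrees of freedom, critical value 2.262 and noncentrality d√10.

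*After-effect 0.05, no familiarisation, no learning:*

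| σ | σ√2 | d | d√10 | Planned contrast significant | Baseline to Baseline significant |
|---|---|---|---|---|---|
| 0.04 | 0.0566 | 0.884 | 2.795 | 70% | 5% |
| 0.06 | 0.0849 | 0.589 | 1.863 | 38% | 5% |
| 0.08 | 0.1131 | 0.442 | 1.398 | 24% | 5% |

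Free of any particular σ: combined shifts of 0.3, 0.5, 0.8 and 1.0 SD of the paired difference give 14%, 29%, 62% and 80% for the planned contrast with no lasting effect.

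*Familiarisation 0.03 plus after-effect 0.03, no learning, σ = 0.04:*

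- Planned: δ = 0.06, d = 1.061, 85% significant.
- Baseline to Baseline: δ = 0.03, d = 0.530, 32% significant. This contrast removes the after-effect but not familiarisation.

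*True learning only, 0.01 per session, σ = 0.04:*

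- Planned: δ = 5 × 0.01 = 0.05, power 70%.
- Baseline to Baseline: δ = 4 × 0.01 = 0.04, d = 0.707, power 51%. Day 5 Baseline is recorded before the fifth session, so it reflects four.

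If all the learning (0.05) were present before session 5, both contrasts would have 70% power.

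**The case against.** The case for leaving the plan alone has real weight.

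- **The contrast is stated openly and is a legitimate pilot target.** Total change to the end of training is a fair quantity. The SAP treats the tether-off walk as a period for checking retention, and Protocol VIII expects any gait benefit to be temporary. This stands, and it is why the planned contrast should stay.
- **SAP 3.1 already gives much of the answer.** The Day 1 comparison estimates a one-session change and the Day 5 comparison estimates the same-session part. Subtracting the latter from the primary recovers the mean between-day change, given one Post Training summary and the same participants. This stands for the mean. It supplies neither a confidence interval nor a test.
- **A reader might infer that Baseline to Baseline should replace the planned test.** The documents do not support that. Protocol section II asks about change after five sessions, while Day 5 Baseline follows only four. It also keeps any familiarisation, and the decomposition would assign session-5 learning to the same-session part.
- **A reader might infer that a positive result is to be expected even if sessions 2 to 5 add nothing.** That goes too far. The single-session study guided load directly onto the paretic limb, whereas this trial applies a horizontal anterolateral force. The earlier five-day study used such a force, but the SAP reports no one-session result for it.
- **A reader might infer that familiarisation inflates the result.** The protocol says only that participants become familiar with the treadmill, not that this raises the paretic to non-paretic ratio.

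**Conclusion.** The concern holds as a gap in analysis and interpretation. The primary load test adds between-day change to Day 5 same-session change, so significance alone cannot be read as improvement accumulated over five sessions. The data needed to estimate the between-day part are already collected, but no inference on it is planned.

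The structure follows from the documents; the size does not. The 24% to 70% range rests on an assumed after-effect of 0.05, assumed occasion SDs of 0.08 to 0.04, independent occasions and 10 completers. The documents do not show that either the after-effect or familiarisation is large, and they give no direction for familiarisation. Nor do they support calling the planned contrast invalid or replacing it.

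**What to change.** In SAP 2.2.1:

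1. Keep Day 1 Baseline to Day 5 Post Training, labelled as total change that includes the same-session after-effect.
2. Add a paired Day 1 Baseline to Day 5 Baseline estimate with 95% CI and test, labelled as carry-over after four sessions that still includes any treadmill familiarisation.
3. Report the decomposition in the same participants, using one stated Post Training summary. The SAP does not say whether Day 5 Post Training is the mean of PT1 to PT4 or one of them. The Post Training recording times also differ (minutes 1, 3, 5, 7 and 9 in Protocol VI.C.ii; four windows in SAP 4.2.1) and should be reconciled.
4. State that accumulated or retained training improvement will be claimed only if the Baseline-to-Baseline change supports it.
5. Add a sensitivity version using BL3 only on both days. It reduces familiarisation but does not remove it. A version starting from Day 2 Baseline would also discard the effect of session 1 and should be labelled so.

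The cost is SAP wording and one extra paired comparison, plus the sensitivity version, on data already recorded; no visit or procedure changes. The added contrast has less power if learning continues into session 5 (51% against 70% in the example above), so a non-significant result there should be read from its interval and not as evidence of no carry-over.
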